#### Apixaban

NON-INTERVENTIONAL STUDY PROTOCOL

plan enrollment with medical and pharmacy benefits (Medicare parts A, B, and D) after the index date;

Note: Revised from no requirement for continuous health plan enrollment post-index date to generate comparable cohorts.

- 3) Patients had CHA2DS2-VASc score  $\geq$ 2 during 12 months on or before the index date;
- 4) Aged  $\geq 65$  years on the index date.

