# 8.2.1. Primary Objective and High-Risk Subgroup Analyses

# 8.2.1.1. Inclusion Criteria

Patients had ≥1 inpatient claim or ≥2 outpatient claims (at least 7 days gap between the two outpatient claims) for AF (ICD-9-CM code 427.31; ICD-10-CM: I480-I482, I4891) during 01JAN2013-31DEC2016. The first AF diagnosis claim dates during the identification period will be designated as the index date;

Note: Revised from  $\geq 1$  AF diagnoses based on literature review and clinical rationale to consolidate the diagnosis of AF.

2) Patients had 12-month continuous health plan enrollment with medical and pharmacy benefits (Medicare Part A, B, and D) before the index date and 6-month continuous health

Do not distribute for purposes outside of specific activities related to development of FDAMAs114 compliant pieces. Content within this protocol is subject to change based on communication planning and input by external review committees.

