## 8.3. Variables

All data will be extracted from the Medicare Database (Section 8.4). Baseline variables will be measured for the prior 12 months through the index date (exclusive of the index date). All relevant ICD-9-CM, ICD-10-CM, and CPT codes are available in the Appendix.

Variable a	Role	Operational definition
Age	Baseline characteristic and potential predictor	Age will be defined as of the index date, retained in the dataset as continuous, and divided by the following age groups: 65-74, 75-84, and $\geq$ 85 years.
Sex	Baseline characteristic and potential predictor	A flag will be created for female beneficiaries on the index date and reported as a percentage.
Race/ethnicity	Baseline characteristic and potential predictor	A flag will be created for White, Black, Hispanic, and other races/ethnicities on the index date.
US geographic region	Baseline characteristic and potential predictor	The US will be divided into 5 regions: Northeast, South, North Central, West, and Other. Geographic region will be captured from enrollment data.

Table 1	. Baseline	Variables
---------	------------	-----------

Do not distribute for purposes outside of specific activities related to development of FDAMAs114 compliant pieces. Content within this protocol is subject to change based on communication planning and input by external review committees.

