#### Apixaban

NON-INTERVENTIONAL	STUDY DDOTOCOL
NON-INTERVENTIONAL	STUDIIKUIUCUL

Variable a	Role	Operational definition	
Index year	Baseline characteristic and potential predictor	A flag will be created for patients with index date in the year of 2013-2016.	
Medicaid dual eligibility	Baseline characteristic and potential predictor	A flag will be created for patients with Medicaid dual eligibility.	
Part-D low income subsidy	Baseline characteristic and potential predictor	A flag will be created for patients with a Part-D low income subsidy.	
Baseline Deyo-Charlson comorbidity index score	Baseline characteristic and potential predictor	The Deyo-Charlson comorbidity index score will be created during the baseline.	
Baseline CHADS2 score	Baseline characteristic and potential predictor	The CHADS 2 score will be used to analyze the effect of stroke risk stratification on OAC use. The maximum score is 6. CHADS 2 scores: 2-3, 4-5, and $\geq 6$ .	
Baseline CHA2DS2-VASc score	Baseline characteristic and potential predictor	The CHADS 2 VASc score will also be used as indicated above. The maximum score is 9. CHADS 2 -VASc scores: 2-3, 4-5, and $\geq 6$ .	
HAS-BLED score	Baseline characteristic and potential predictor	The HAS-BLED score will be used to estimate the risk of major bleeding. As the INR value is not available in the databases, a modified HAS-BLED score was calculated with a range of 0 to 8.	
Baseline prior bleed	Baseline characteristic and potential predictor	A flag will be created for patients with a bleeding- related claim during the baseline period.	
Baseline prior stroke/SE	Baseline characteristic and potential predictor	A flag will be created for patients with a stroke/SE claim during the baseline period.	
Obesity	Baseline characteristic and potential predictor	A flag will be created for patients with obesity claims during the baseline.	

Do not distribute for purposes outside of specific activities related to development of FDAMAs114 compliant pieces. Content within this protocol is subject to change based on communication planning and input by external review committees.

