# Logistic Regression: Predictors for OAC Treatment/non-treatment (Primary Objectives)

A logistic regression will be used to examine risk factors associated with OAC treatment (OAC, DOAC, or warfarin)/non-treatment with OACs and DOAC treatment/warfarin treatment. Predictor data will be examined during the 12 months baseline period before the index date.

Stepwise model selection will be used to identify risk factors. The final covariate lists will be finalized based on clinical rationale and model fitting.

Odds ratios, p-values, and 95% confidence intervals (CIs) for all model covariates will be provided. Diagnostic tests will be performed for the multivariate models. Hosmer-Lemeshow tests will be performed and the area under the Receiver Operating Characteristic curve will be checked.

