# 8.8. Subgroup and Sensitivity Analysis

Additional subgroup and sensitivity analyses will be conducted, including:

- high-risk CHA2DS2-VASc score subgroups, specifically, 2-3, 4-5, and ≥6 (primary objective): assess whether the predictors of treatment would be impacted by baseline CHA2DS2-VASc score.
- high-risk age subgroups, specifically, 65-74, 75-79, and  $\geq$ 80 years (primary objective): assess whether the predictors of treatment would be impacted by age.
- censor patients at 6 months (secondary clinical objectives): assess whether the differential follow-up time in each cohort would affect the clinical outcomes.
- use a certain allowable gap for drug exposure, such as 14 days (secondary clinical objectives): assess whether the allowable gap in OAC days of supply for treated patients would have an impact on the clinical outcomes, since a shorter allowable gap will increase the likelihood of having the patients truly on treatment.
- multivariable Cox regression (secondary clinical objectives): assess whether statistical methods on the multivariable analysis would affect the clinical outcomes.
- adjusting for the competing risks of death (secondary clinical objectives): assess whether death is a competing risk in the clinical outcome analyses.

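### CHA2DS2-VASc is scored with the index date for entry but without it as predictor and subgroup variable, so the two scores can differ and some eligible men aged 65-74 fall in no band

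*Protocol*

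**What the plan says.** **Entry.** Protocol 8.2.1.1, criterion 3, takes the score "during 12 months on or before the index date". The index date is the date of the first AF claim: "The first AF diagnosis claim dates during the identification period will be designated as the index date". One inpatient claim is enough to qualify.

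**Baseline variables.** Section 8.3 states: "Baseline variables will be measured for the prior 12 months through the index date (exclusive of the index date". Table 1, in that section, lists the baseline CHA2DS2-VASc score as a potential predictor, with bands 2-3, 4-5 and 6 or more. It also lists flags for prior stroke/SE, heart failure, hypertension, diabetes, myocardial infarction, peripheral arterial disease and coronary artery disease.

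**Primary model.** Section 8.7, on the logistic regression, states: "Predictor data will be examined during the 12 months baseline period before the index date".

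**Subgroups.** Section 8.8 uses the same three bands to "assess whether the predictors of treatment would be impacted by baseline" CHA2DS2-VASc score. Section 7 gives the same bands.

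**Age.** Table 1: "Age will be defined as of the index date". The minimum age of 65 is also set in "years on the index date".

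Nothing in the protocol gives the score a window that includes the index date when it serves as predictor or subgroup variable.

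**The concern.** One named score does three jobs: entry threshold, candidate predictor and subgroup variable. The protocol fixes its window twice, and the two windows disagree. An analyst who follows the text computes two values per patient under one name.

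The primary objective is to identify predictors of OAC treatment, overall and within score bands. If a stroke is first coded on the same date as the AF, it earns two points at entry. In the model it earns no stroke points and leaves the prior stroke/SE flag at zero. The discrepancy runs one way only, because the modelled score can be too low but never too high relative to the entry score. It arises only in patients with a component newly coded at index.

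**Working it through.** **Inputs**
- Entry window: 12 months, index date included (8.2.1.1, criterion 3).
- Baseline and predictor window: 12 months, index date excluded (8.3, 8.7).
- Subgroup score: the baseline score (8.8), which is defined only in Table 1.
- Weights, read from the score's name and the abbreviation list: heart failure 1, hypertension 1, age 75 or over 2, diabetes 1, stroke 2, vascular disease 1, age 65-74 1, sex 1. The age items exclude each other, so the maximum is 1 + 1 + 2 + 1 + 2 + 1 + 1 = 9. This agrees with Table 1: "The maximum score is 9".
- Assumptions: the sex point goes to women, and both windows start on the same day.

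**Step 1: the two scores**

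Entry score = age points + sex point + weights of components coded before or on the index date.

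Modelled score = age points + sex point + weights of components coded before the index date.

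Entry score − modelled score = weights of components first coded on the index date. Age and sex cancel. The difference is never negative, and it is at least 1 whenever such a component exists.

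**Step 2: who can fall below the lowest band**

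Points from age and sex alone:
- man 65-74: 1 + 0 = 1
- woman 65-74: 1 + 1 = 2
- man 75 or over: 2 + 0 = 2
- woman 75 or over: 2 + 1 = 3

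Only a man aged 65-74 with no earlier coded component can have a modelled score below 2. If hypertension is first coded at index, he enters with 1 + 1 = 2 and is modelled with 1. If it is stroke, he enters with 1 + 2 = 3 and is modelled with 1. In both cases he is eligible and has no band.

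**Step 3: band shifts in other patients**

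Take a woman aged 75 or over with earlier hypertension. Her modelled score is 3 + 1 = 4, band 4-5. With stroke first coded at index, her entry score is 4 + 2 = 6, band 6 or more.

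**Step 4: all profiles**

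Two age groups × two sexes × 2^5 comorbidity patterns give 128 profiles. Each of the five components is absent in half of them (64), so adding one absent component on the index date gives 5 × 64 = 320 combinations. The entry score exceeds the modelled score in all 320. The band differs in 165:
- 65 are modelled in 2-3 but enter in 4-5
- 95 are modelled in 4-5 but enter in 6 or more
- 5 are modelled below 2 but enter in 2-3 (all men aged 65-74, one for each component)

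These count possible profiles and are not patient frequencies.

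**Step 5: one window**

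With a common window the difference in step 1 is zero for every patient, and criterion 3 guarantees that nobody lies below 2.

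**The case against.** **The split follows a pattern.** The valve disease, VTE and transient AF exclusions also include the index date, while covariates are taken before it. Eligibility up to and including index with pre-index predictors is a defensible design in general. That stands for variables that serve only one purpose. It does not rescue a score whose entry threshold is also the floor of its bands.

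**The wording is awkward.** Section 8.3 says both through the index date and exclusive of it, and bands that start at 2 suggest that the authors had one score in mind. This is fair, and it supports stating one window. As written, however, the parenthesis in 8.3 and the sentence in 8.7 both point to exclusion.

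**The effect is narrow.** This stands. Age, sex and race/ethnicity are already set on the index date, so it is not true that every predictor is measured strictly before it. Women, and everyone aged 75 or over, stay eligible under either window; only their comorbidity values and band can change.

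**Treatment may start long after index.** This also stands. Under 8.2.3, a patient is ever-treated with any OAC claim on or after the first AF diagnosis up to the end of 2016. A reader might infer that the treatment decision is always made with the index-date diagnoses in hand and nothing later. The protocol does not fix that, and including one more day does not capture everything known at a later start.

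**A size might be inferred.** A reader could assume a score distribution and a rate of new coding at index and derive a percentage of patients in the wrong band. The protocol gives neither figure. Nor would the whole-cohort score distribution apply to affected patients: a woman aged 65-74 or a man aged 75 or over who enters with exactly 2 has no comorbidity point to lose. The ratio 165/320 is not such a percentage either.

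**Conclusion.** The contradiction is real and nothing in the protocol resolves it. Followed as written, every patient with a comorbidity component first coded on the index date is modelled on a score below the entry score, by 1 point or by 2 for stroke when one component is new. Some of them move to a lower band. Men aged 65-74 with no earlier coded risk factor are eligible but belong to no band.

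The number affected cannot be estimated from the document, nor can the direction or size of any change in the odds ratios. New coding on that date is plausible, because the index can be an inpatient claim. Sample size and error rates are untouched. The conclusion rests on the literal windows in 8.2.1.1, 8.3 and 8.7 and on the weights and assumptions listed above. It should be corrected before the multivariate analysis, but it does not undermine the study.

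**What to change.** For the primary objective and the high-risk subgroups, define one window for CHA2DS2-VASc and its component flags: the 12 months before through and including the index date, as criterion 3 already does. Use that single score for entry, as predictor and for the 2-3, 4-5 and 6-or-more bands. Amend the window sentence in 8.3 and the predictor sentence in 8.7 to match.

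Apply the same window to the other diagnosis-based predictors in the primary model (CHADS2, HAS-BLED, the Charlson index and the remaining comorbidity flags), so that no new split arises between the score and the other predictors. The prior stroke/SE flag would then mean on or before index and should be labelled so. Because outcomes for secondary objectives 2-5 are timed from the index date, 8.3 should say that the change applies to the primary and subgroup analyses only.

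The cost is small: edits to two sections and a change to the look-back code. There are two downsides. Some index-date codes may be work-up diagnoses, a risk that criterion 3 already carries. The same Table 1 flags will also have a different window in the secondary analyses, which must be stated.

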## 8.2.1.2. Exclusion Criteria

- 1) Exclude patients with AF diagnosis prior to the index date;
- 2) Exclude patients with medical claims indicating diagnosis of mitral valvular heart disease or valve replacement procedure (see Appendix) during the 12 months prior to or on the index date;
- 3) Exclude patients who had a pharmacy claim for apixaban, dabigatran, edoxaban, rivaroxaban, or warfarin during the 12 months pre-index period.

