For the primary and secondary objectives, the first AF diagnosis date during the identification period will be used as the index date for both ever-treated and never-treated cohorts. Across both ever-treated and never-treated cohorts, all patients will be required to have a  $CHA_2DS_2$ -VASc $\geq 2$  and 12-months of continuous health plan enrollment, with medical and pharmacy benefits before the index date (baseline period). For the primary objective and high-risk subgroup analyses, patients will also be required to have 6-month continuous health plan enrollment, with medical and pharmacy benefits after the index date.

For the primary objective and high-risk subgroup analyses, the following patients will be excluded: an AF diagnosis any time prior to the first AF diagnosis; medical claims indicating a diagnosis or procedure for mitral valvular heart disease or heart valve replacement/transplant;

Do not distribute for purposes outside of specific activities related to development of FDAMAs114 compliant pieces. Content within this protocol is subject to change based on communication planning and input by external review committees.

Apixaban NON-INTERVENTIONAL STUDY PROTOCOL

or use of OACs during the baseline period. For the secondary objective assessing effectiveness, safety, and cost outcomes, patients will be further excluded if they had any of the following: venous thromboembolism; transient AF during the baseline period; pregnancy during the study period; hip/knee replacement surgery within 6 weeks pre-index date; or follow-up period = 0 day. In addition, among patients ever treated with an OAC, those with >1 OAC prescription claim at the index date will be excluded as well.

**Variables:** Baseline demographic and clinical characteristics will include age, gender, race, geographic region, Medicaid dual eligibility, Part-D low income subsidy, Charlson comorbidity index (CCI), CHADS2, CHA2DS2-VASc, HAS-BLED scores, prior bleeding/stroke events, congestive heart failure, diabetes, hypertension, chronic obstructive pulmonary disease, renal disease, myocardial infarction, dyspepsia or stomach discomfort, peripheral arterial disease, transient ischemic attack, coronary artery disease, history of falls, medication use, and index dose of DOAC. Baseline all-cause health care costs and utilization will be included.

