# 8. Research Methods

# 8.1. Study Design

The study will be a longitudinal retrospective cohort analysis using the US fee-for-service (FFS) Medicare database. This database contains data from inpatient departments, outpatient departments, carrier claims, reported drug events, and beneficiaries' enrollment data. The following will be determined and compared between treatment status (treated with apixaban, dabigatran, edoxaban, rivaroxaban, or warfarin and untreated with OAC): outcomes including major bleeding, stroke/SE, and death; and health care costs and resource utilization. The overall study period will be from 01JAN2012-31DEC2016. The study will designate a 12-month baseline period prior to an index identification period (01JAN2013-31DEC2016). The date of first AF diagnosis during the study period will be assigned as the index date.

Figure 1. Study Periods for Primary and High-Risk Subgroup Objectives

(for illustration purposes only, may not be proportional)

Do not distribute for purposes outside of specific activities related to development of FDAMAs114 compliant pieces. Content within this protocol is subject to change based on communication planning and input by external review committees.

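### The prior-AF exclusion has no fixed window, so the AF-free screen behind 'newly diagnosed' lengthens with index year; this tends to inflate the never-treated share and adds an artefact to the index-year predictor

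*Protocol*

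**What the plan says.** Protocol 8.1 sets the data window, "The overall study period will be from 01JAN2012-31DEC2016", and the index window, "The study will designate a 12-month baseline period prior to an index identification period (01JAN2013-31DEC2016". Under 8.2.1.1, "The first AF diagnosis claim dates during the identification period will be designated as the index date".

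Exclusion 1 in 8.2.1.2 reads "Exclude patients with AF diagnosis prior to the index date". The abstract states the same exclusion as "an AF diagnosis any time prior to the first AF diagnosis". Neither gives a length. The other two exclusions in that list are bounded: valve disease is searched over 12 months, and prior OAC use covers "rivaroxaban, or warfarin during the 12 months pre-index period".

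Enrollment is guaranteed for one year before index: "Patients had 12-month continuous health plan enrollment with medical and pharmacy benefits (Medicare Part A, B, and D) before the index date". The primary objective also requires six months of enrollment after index.

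Table 1 in 8.3 lists index year as a baseline characteristic and potential predictor: "A flag will be created for patients with index date in the year of 2013-2016". Section 6 gives the prevalence of untreated patients among those newly diagnosed as a study aim. Neither the sensitivity analyses in 8.8 nor the limitations in 8.10 mention a look-back that varies with index year.

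**The concern.** The rule that decides who counts as newly diagnosed is the only one of the three exclusions without a fixed length, and the data start imposes a length that grows with index date. A patient with AF before 2012 and no AF claim for a little over a year can be indexed in 2013 as new. In 2016 the same patient, if continuously observed, would need a gap of at least four years; otherwise the intervening claim would exclude the patient or fix an earlier index date.

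The patients who slip through are a selected group. Exclusion 3 removes anyone with an OAC claim in the preceding 12 months, so each has had AF for more than a year and no OAC claim for at least a year. Such patients are more likely than truly new patients to stay untreated.

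Two primary results are exposed: the share of newly diagnosed patients never treated, and the odds ratio for index year, which then carries the length of the AF screen as well as any change in prescribing.

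**Working it through.** **1. Length of the screen.** Look-back ceiling = index date minus 01JAN2012. The earliest index date, 01JAN2013, gives 12 months, matching the baseline period in 8.1. For the primary objective, six months of post-index enrollment in data ending 31DEC2016 put the last usable index date at about 30JUN2016. Time available to become ever-treated = 31DEC2016 minus index date.

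| Index year | AF-free screen, ceiling (months) | Midpoint | Time to become ever-treated, at most (months) |
|---|---|---|---|
| 2013 | 12-24 | 18 | 36-48 |
| 2014 | 24-36 | 30 | 24-36 |
| 2015 | 36-48 | 42 | 12-24 |
| 2016 | 48-54 | 51 | 6-12 |

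The midpoint ratio, 2016 to 2013, is 51/18 = 2.8. With only 12 months of prior enrollment guaranteed, the floor is 12 months in every year.

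**2. Possible size of the leak: assumptions only.** The protocol gives none of these inputs. Assume a prevalent AF pool of P = 2 to 5 times yearly incident AF, 30% of it OAC-free, an AF-claim rate λ = 0.5 to 2 per year, constant incidence, and a never-treated share of 40% in truly new and 80% in leaked patients. With a and b the start and end of the index window in years since 01JAN2012:

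L = 0.3·P·(e^(-λa) − e^(-λb))/(b − a); leaked share c = L/(1 + L); never-treated share = 0.40 + 0.40c.

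Example, λ = 0.5, P = 5, index year 2013 (a = 1, b = 2): L = 1.5 × (0.6065 − 0.3679) = 0.358; c = 0.358/1.358 = 26.4%; never-treated share 50.5%.

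| λ, P | c 2013 | c 2016 (a = 4, b = 4.5) | Never-treated 2013 | Never-treated 2016 | Pooled (a = 1, b = 4.5) |
|---|---|---|---|---|---|
| 2, 2 | 6.6% | 0.0% | 42.6% | 40.0% | 40.9% |
| 1, 5 | 25.9% | 2.1% | 50.3% | 40.8% | 45.3% |
| 0.5, 5 | 26.4% | 8.2% | 50.5% | 43.3% | 47.1% |

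The true share is 40% throughout. The model gives every patient the full calendar look-back, which overstates the contrast between years.

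**3. The opposing effect, also on assumptions.** Never-treated means no OAC claim through 31DEC2016. Suppose 50% are untreated at 9 months (midpoint of 6-12) and 2-5% per year start later, ignoring death and disenrollment. The 2013 midpoint is 42 months, so the extra time is 33 months = 2.75 years:

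- 2% per year: 0.50·e^(-0.055) = 47.3% never-treated in 2013; treatment odds ratio, 2016 versus 2013, = 1/(0.527/0.473) = 0.90.
- 5% per year: 0.50·e^(-0.1375) = 43.6%; odds ratio = 1/(0.564/0.436) = 0.77.

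The leak alone moves this odds ratio above 1; unequal time to start treatment moves it below 1.

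**4. A shorter exclusion window alone does not equalise the screen.** Index is the first AF claim since 01JAN2013, so limiting exclusion 1 to 12 months would still leave an AF-free span of 12 months for 2013, 12-24 for 2014, 24-36 for 2015 and 36-42 for 2016. The index date must be redefined too.

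**The case against.** Using all available history above a guaranteed 12 months removes more prevalent AF than a short fixed window would. That is a defensible choice for the main analysis, and it stands.

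A calendar trend is not a stated objective. Index year is only a candidate predictor, subject to stepwise selection and clinical judgement (8.7), and keeping it may absorb some era-related leakage from other odds ratios. This lowers the stakes, but does not help anyone who reads the index-year odds ratio as a prescribing trend.

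Entry requires one inpatient or two outpatient AF claims at least seven days apart, and secondary diagnosis codes count unless specified otherwise. The first filters out low-contact patients; the second makes long AF-claim gaps rarer. Both shrink the leak by an unknown amount, so the effect could be negligible.

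A reader might infer that treatment will appear to rise over calendar time by construction, or that the early-year never-treated share must be too high on balance. The protocol does not support either as a net claim, because longer time to start an OAC lowers the never-treated share in early years. A reader might also take 48-60 months as the 2016 screen, or assume every 2016 patient receives it. The six-month post-index requirement caps the primary analyses at 54 months, and 12 months of enrollment suffice for entry.

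**Conclusion.** The defect stands as a matter of design. The maximum AF-free screen rises from 12-24 months in 2013 to 48-54 months in 2016, varies between patients within a year, and is not addressed in 8.8 or 8.10.

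For the pooled never-treated share the direction is clear, provided leaked patients are more often never-treated than new ones: leakage raises it, and the short follow-up of late index dates raises it too, so the two do not offset. For index year, the two artefacts pull in opposite directions and the net sign is undetermined. No size can be derived from the protocol; the figures in steps 2 and 3 only show that either artefact could matter, or be small, under assumed inputs. This warrants an added sensitivity analysis and a restriction on interpretation, not a redesign.

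**What to change.** Add to 8.8 a sensitivity analysis of the primary objective with index dates from 01JAN2014, 24 months of Part A, B and D enrollment before index, and the index defined as the first AF claim preceded by 24 AF-free months. In that analysis the 24-month rule replaces the open-ended exclusion 1.

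Report the overall never-treated share under both this rule and the main rule. Interpret index-year odds ratios only from this analysis, and only with OAC treatment ascertained over the same period after index for every patient, for example the six months of enrollment already required. Equal look-back alone would still leave up to 24-36 months to start treatment for 2014 against 6-12 for 2016. If this is not done, do not present the index-year odds ratios as a prescribing trend.

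In the same edit, reconcile 8.1, which takes the first AF diagnosis in the study period (and so includes 2012) as the index date, with 8.2.1.1, which uses the identification period.

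Cost: a short protocol addition and one further run on data already held. The analysis loses 2013 index dates and patients with under 24 months of prior enrollment, mainly those aged 65-66. That loss is minor in a 100% Medicare file.
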